4.5. Dose Limiting Toxicity (DLT) Definition

A DLT is defined as the occurrence of any of the following toxic reactions that are considered to be causally related to 3D185 by the PI within the first 35 days after the first dose.

- 1. Hematological toxicity:
 - 1. Grade 4 hematologic toxicity;
 - 2. Grade 3 febrile neutropenia (defined as ANC < $1,000/\text{mm}^3$, a single temperature of >

38.3 \mathbb{C} or a sustained temperature of \geq 38 °C for more than 1 hour) or Grade 3 neutropenia

lasts for more than 7 days with or without drug intervention;

3. Grade 3 thrombocytopenia with bleeding or require to platelet transfusion;

- 2. Non-hematologic toxicity:
 - 4. Any Grade ≥ 3 non-hematologic toxicity (except the following conditions that can be controlled by symptomatic treatment within 48 hours: nausea, diarrhea, vomiting, and electrolyte imbalance [except serum phosphorus]; Grade 3 fatigue with duration ≤ 7 days; Grade 3 hypertension that can be self-resolved or controlled by drugs to below 140/90 mmHg or baseline level within 72 hours);
 - 5. Serum phosphorus ≥7 mg/dL that is unable to recover to < 7 mg/dL within 14 days after phosphorus removal;
 - 6. With liver metastasis or baseline transaminase abnormalities: ALT/AST > 8 × ULN; without liver metastasis or baseline transaminase abnormalities: ALT/AST > 5 × ULN ;
 - 7. 3D185-related AEs that resulted in dose interruption of 3D185 for \geq 7 days in the first treatment cycle.

If the DLT is clinically recovered to Grade 0-1 within 28 days, the subject can resume the treatment of 3D185. If the subject can resume treatment, the Investigator may refer to the provisions of Section 6.3 (Precautions and Dose Modifications) for dose modifications to the same dose or reduce by one dose level.

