In case of Grade 2 AST/ALT elevation in patients without liver metastasis or AST/ALT elevation \geq 3.0-5.0 folds over baseline value in patients with liver metastasis, withhold 3D185 until the level returns to grade \leq 1 or baseline, and the liver test should be evaluated at least twice a week. Restart treatment with 3D185 at the same dose level.

In case of total bilirubin ≥ 2 folds over ULN, withhold 3D185 until the level returns to CTCAE Grade ≤ 1 or baseline, and the liver test should be evaluated at least twice a week. Restart treatment with 3D185 at same dose level.

In case of Grade 3 AST/ALT elevation, subjects should withhold 3D185 until the AST/ALT level returns to CTCAE Grade ≤ 1 or baseline. If the AE resolves within 7 days, dosing may resume at the same dose level. If the AE resolves within 7-14 days, dosing may resume at the previous lower dose level or may be modified according to the Investigator's judgment. If the AE cannot resolve within 28 days, the treatment of 3D185 will be permanently discontinued. Liver enzymes should be monitored once a week when the subject receives 3D185 treatment again.

When a hepatic injury is suspected due to abnormal liver function test (such as Grade ≥ 3 AST/ALT elevation), it is recommended to perform a comprehensive assessment (liver imaging, liver function tests and pathogen tests, etc.) as soon as possible.

Abnormal values in AST and/or ALT concurrent with abnormal elevations in total bilirubin that meet the criteria outlined below in the absence of other causes of liver injury are considered

potential cases of drug-induced liver injury (potential Hy's law cases) and should always be considered important medical events, 3D185 must be discontinued immediately. The threshold of laboratory abnormalities for a potential case of drug-induced liver injury depends on the subject's individual baseline values and underlying conditions. Subjects who present with the following laboratory abnormalities (potential drug-induced liver injury) should be evaluated further to determine the etiology of the abnormal laboratory values definitively:

- Subjects with AST or ALT and total bilirubin baseline values within the normal range who subsequently present with AST or ALT values ≥ 3 folds over ULN concurrent with a total bilirubin value ≥ 2 folds over ULN with no evidence of hemolysis and an alkaline phosphatase value ≤ 2 folds over ULN.

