6.3.3. Discontinuation criteria for study treatment

When the following 3D185 related severe or life-threatening AEs occur, the investigational product must be permanently discontinued.

- Drug-related Grade 3 AEs or Grade 2 CSR/RPED that cannot recover to Grade ≤ 1 or baseline levels by symptomatic treatment within 28 days;
- Any grade 4 toxicities;
- Recurrent ≥ 2 Grade proteinuria;
- Recurrent Grade 3 eye toxicity associated with vision changes;
- Hy's law confirmed drug-induced liver injury;
- Grade 2 hypercalcemia concurrent with hyperphosphatemia or ≥ Grade 3 hypercalcemia in absence of hyperphosphatemia;
- Other AEs that the Investigator judged to be inappropriate to continue dosing.

If a subject has been deriving benefit from treatment, and the investigator can demonstrate that reintroduction of study drug is in the best interest of the subject considering the terminal nature of the disease, the drug may be re-introduced at a lower dose and/or intensity if the medical monitor is in agreement with this assessment. With appropriate re-consenting, the subject can be retreated with a 2-dose level reduction as appropriate, along with appropriate clinical follow-up as designated by the investigator.

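### Section 6.3.1 gives overlapping restart rules for raised AST/ALT in liver-metastasis subjects with a raised baseline, and its uncapped bilirubin rule collides with the Grade 4 stop in 6.3.3

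*Protocol*

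**What the plan says.** The Hepatotoxicity Management Guideline in Protocol section 6.3.1 has three hold-and-restart rules.

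- **AST/ALT, lower tier.** This applies to Grade 2 elevation without liver metastasis, or to elevation of "3.0-5.0 folds over baseline value in patients with liver metastasis". After recovery: "Restart treatment with 3D185 at the same dose level".
- **Bilirubin.** "In case of total bilirubin ≥ 2 folds over ULN, withhold 3D185 until the level returns to CTCAE Grade ≤ 1 or baseline". Treatment then restarts at the same dose. No upper limit is given.
- **Grade 3 AST/ALT, all subjects.** "In case of Grade 3 AST/ALT elevation, subjects should withhold 3D185 until the AST/ALT level returns to CTCAE Grade ≤ 1 or baseline". Then: "If the AE resolves within 7 days, dosing may resume at the same dose level". Next: "If the AE resolves within 7-14 days, dosing may resume at the previous lower dose level", and that sentence goes on to allow modification on the investigator's judgment instead. Treatment stops permanently if the event has not resolved within 28 days. Recovery between 14 and 28 days is not mentioned.

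Section 5.2, criterion 7, admits liver-metastasis subjects with ALT/AST up to 5 × ULN. Section 6.3.2 gives general rules in Table 6, sends liver toxicity to 6.3.1, and limits holds for drug-related events to 28 days, with a stated exception. Section 6.3.3 requires permanent discontinuation for drug-related events that include "Any grade 4 toxicities". Its exception re-introduces the drug only at a lower dose and/or intensity.

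**The concern.** The lower AST/ALT tier is measured against the subject's own baseline in liver-metastasis subjects, while the Grade 3 paragraph uses CTCAE grade and covers everyone. When the baseline is already raised, one AST/ALT value can meet both triggers, and the two paragraphs do not give the same restart instruction for every recovery time. The bilirubin sentence has no ceiling, so it reaches values for which another section orders a permanent stop. No text ranks the three liver rules, or ranks 6.3.1 against 6.3.3.

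Section 6.3.1 itself lists liver function abnormalities among the toxicities expected from preclinical work, so sites are likely to need these rules. Two sites reading the same protocol correctly could restart identical subjects at different doses, or restart one and stop the other.

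**Working it through.** There is no sample-size or power figure to reproduce. The check compares thresholds and sets the passages side by side.

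**Inputs.** Baseline AST/ALT = b × ULN, with b up to 5 (section 5.2, criterion 7). The lower-tier trigger is 3.0–5.0 times baseline (section 6.3.1). Grading follows CTCAE v4.03 (section 8.5.1), whose AST/ALT cut-offs are not printed in the protocol. *Assumption:* Grade 3 starts above c × ULN, with c = 5 as the main case and 8 and 10 as a sensitivity range.

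**Step 1: the band in ULN units.** Lower limit 3b, upper limit 5b.

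- b = 1: 3–5 × ULN
- b = 2: 6–10 × ULN
- b = 3: 9–15 × ULN
- b = 5: 15–25 × ULN

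**Step 2: overlap with Grade 3.** Part of the band exceeds c when 5b > c, that is b > c/5. All of it exceeds c when 3b > c, that is b > c/3.

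| Assumed cut-off c (× ULN) | Overlap starts, b > c/5 | Whole band above c, b > c/3 |
|---|---|---|
| 5 | 1.0 | 1.67 |
| 8 | 1.6 | 2.67 |
| 10 | 2.0 | 3.33 |

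Every entry lies inside the eligible range (b ≤ 5). At c = 5 there is no overlap for b ≤ 1.0. The tiers can also invert: at b = 3 the lower tier begins at 9 × ULN, although Grade 3 is assumed to begin above 5 × ULN.

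**Step 3: what each AST/ALT rule then says.**

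| Recovery time | Baseline-multiple rule | Grade 3 paragraph |
|---|---|---|
| Within 7 days | Same dose | Same dose allowed |
| 7–14 days | Same dose | Lower dose, or investigator-judged modification |
| 14–28 days | Same dose | Nothing stated |
| Unresolved at 28 days | No limit of its own; the 6.3.2 limit applies to drug-related holds | Permanent stop |

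The rules agree up to day 7 and diverge after it.

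**Step 4: the 14–28 day gap.** Table 6 has a Grade 3 row covering any recovery within 28 days, with restart one or two doses lower. If Table 6 applies to liver events in general, it contradicts the 7-day same-dose option in 6.3.1. If it is only a default where 6.3.1 is silent, it fills the gap. Section 6.3.2 refers liver toxicity to 6.3.1 without saying which is meant.

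**Step 5: bilirubin.** This needs no exact cut-off, only that Grade 4 lies above 2 × ULN. A trigger from 2 × ULN upwards with no ceiling then includes every Grade 4 value. A drug-related Grade 4 rise therefore meets a same-dose restart in 6.3.1 and a permanent stop in 6.3.3, whose exception does not allow the same dose. Combined AST/ALT and bilirubin rises that meet the Hy's law criteria have their own discontinuation text in 6.3.1, so the conflict concerns isolated bilirubin rises.

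**The case against.** The best defence is that the practical conflict is narrow, and much of this is right. The two AST/ALT rules agree for recovery within 7 days. At 7–14 days the Grade 3 paragraph is permissive and leaves room for judgment, so it does not forbid the same dose. Table 6 may be a natural default for 14–28 days. For Grade 4 bilirubin, the mandatory list in 6.3.3 plausibly overrides a guideline sentence that never mentions Grade 4. What remains is that the protocol states none of these precedences, and that a plain same-dose instruction and a conditional one still apply to the same value.

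Three stronger readings are tempting, but the documents do not support them.

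- *The lower tier allows restart after a hold of any length.* Sections 6.3.2 and 6.3.3 limit this to 28 days for drug-related events, subject to the stated exception.
- *The band contradicts the dose-limiting toxicity limit*, "With liver metastasis or baseline transaminase abnormalities: ALT/AST > 8 × ULN". That limit classifies events for escalation and is not a restart threshold. Section 4.5 expressly allows resumption at the same dose, or one level lower, after a DLT that recovers to Grade 0–1 within 28 days. The value 8 appears in the working only as a sensitivity cut-off.
- *Subjects with a high baseline could have very high ALT with no hold until 3b is reached.* With Grade 3 assumed above 5 × ULN, the Grade 3 paragraph already requires the hold.

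**Conclusion.** The point holds as a wording conflict in a safety rule. With Grade 3 assumed to start above 5 × ULN, the two AST/ALT rules overlap for liver-metastasis subjects whose baseline exceeds 1.0 × ULN, and the whole baseline-multiple band lies above the cut-off once baseline exceeds 1.67 × ULN. Assumed cut-offs up to 10 × ULN move these points to 2.0 and 3.33, still within eligibility. The consequence is limited to recovery beyond 7 days, and a normal baseline produces no collision. The documents give no baseline distribution, so the number of subjects affected cannot be stated.

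The bilirubin conflict with 6.3.3 does not depend on the AST/ALT cut-offs. It is confined to isolated, drug-related Grade 4 rises. Whether Table 6 governs Grade 3 AST/ALT recovery between 14 and 28 days is unresolved in the text.

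**What to change.** Reconcile the AST/ALT and bilirubin paragraphs of 6.3.1 with each other, with Table 6 and with 6.3.3, so that each liver value and each recovery time falls under one rule only. State which section takes precedence where two could apply, and whether Table 6 applies where 6.3.1 is silent. Which restart or stopping rule stands is for the sponsor to decide; this review takes no view on it.

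The cost is rewording at the next amendment. No new assessments are needed.

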During the study, once the urinary protein test $\geq 2+$ (Grade ≥ 2 proteinuria), the subject should withhold 3D185 with 24-hour urine protein quantitative test and urine sediment test to detect microscopic hematuria. Dosing may continue while waiting for test results. If urine protein <

2 g/24 h, dosing may resume at the same dose level and it is recommended to continuously monitor urine protein. If urine protein ≥ 2 g/24 h, withhold until urine protein is < 2 g/24 h, restart at the same dose level or previous lower dose level per Investigator judgment. If Grade ≥ 2 proteinuria persists more than 28 days, the treatment of 3D185 should be permanently discontinued.

If the urinary protein test $\ge 2+$ (Grade ≥ 2 proteinuria) experience second recurrence or nephrotic syndrome occurs, 3D185 should be permanently discontinued.

A nephrologist is recommended to consult, when any Grade 3 proteinuria or other risk factors (e.g., microscopic hematuria, high blood pressure, etc.) occur.

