6.3.2. Dose Delay/Dose Modification

During the DLT evaluation period of the dose escalation phase, subject can withhold 3D185 due to drug-related AEs. If the withholding time is more than 7 days, the AE will be considered as DLT. Unless DLT occurs, subject's dose of 3D185 will not be reduced during this period.

Treatment can be modified or terminated based on toxicity as described in Table 6. For phosphate, liver, eye, kidney toxicity, specific recommendations in the management guidelines are provided in Section 6.3.1.

Toxicity Grade	Action	Dose Modification After Resolution of Adverse Event
1	None	Continue same dose
2	None or consider withheld or discontinue	If withheld, restart at same dose or 1 dose lower, if necessary.
3	Withheld	Restart at 1 or 2 doses lower if recovery (to \leq Grade 1 or back to baseline for non-hematologic toxicity) is within 28 days. Discontinue drug if unresolved for >28 days.
4	Withheld or discontinue	Discontinue*

Table 6Dose Modification Guidelines

For general toxicity management:

- Subjects with any grade of toxicity (Grade 1 to 4) should be provided symptomatic treatment when applicable.
- Subjects may have more than 1 dose reduction.

- If 3D185 must be withheld for more than 28 days for a drug-related adverse event that fails to resolve to acceptable level (e.g., ≤ Grade 1 non-hematologic toxicity or back to baseline), treatment with 3D185 should be discontinued with the exception noted below.*
- In all cases of clinically significant impaired wound healing or imminent surgery or potential bleeding complications, it is recommended that dose administration be interrupted, appropriate clinical laboratory data be carefully monitored, and supportive therapy administered, where applicable. Dose administration may be restarted when it is considered safe and at an appropriate dose, according to the investigator's assessment.

*Exception: if a subject has been deriving benefit from treatment, and the investigator can demonstrate that re-introduction of study drug is in the best interest of the subject considering the terminal nature of the disease, the drug may be re-introduced at a lower dose and/or intensity if the medical monitor is in agreement with this assessment. With appropriate re-consenting, the subject can be retreated with a 2-dose level reduction as appropriate, along with appropriate clinical follow-up as designated by the investigator.

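### Protocol 6.3.1 tells sites both to withhold 3D185 and that they may dose while a 24-hour urine protein result is pending, and its literal stop for repeat proteinuria comes one episode later than the mandatory stop in 6.3.3

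*Protocol*

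**What the plan says.** Protocol Section 6.3.1, under nephrotoxicity, treats a urine protein result of 2+ or more as Grade 2 or higher proteinuria and sets out these steps.

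- At that result, "the subject should withhold 3D185 with 24-hour urine protein quantitative test and urine sediment test" are to be done together.
- The next sentence reads: "Dosing may continue while waiting for test results".
- If the 24-hour result is below 2 g, "dosing may resume at the same dose level and it is recommended to continuously monitor urine protein".
- If it is 2 g or more, the instruction is to "withhold until urine protein is < 2 g/24 h", then restart at the same or the previous lower dose.
- If such proteinuria should "experience second recurrence or nephrotic syndrome occurs, 3D185 should be permanently discontinued". Proteinuria persisting beyond 28 days is also a permanent stop.

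Section 6.3.2 gives general rules in Table 6. At Grade 2 the action is "None or consider withheld or discontinue". The same section adds: "For phosphate, liver, eye, kidney toxicity, specific recommendations in the management guidelines are provided in Section 6.3.1". For the DLT period it states: "If the withholding time is more than 7 days, the AE will be considered as DLT".

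Section 6.3.3 lists 3D185-related events for which the product must be permanently discontinued. Recurrent proteinuria of Grade 2 or higher is among them. An exception follows for subjects who benefit: re-introduction at a lower dose and/or intensity, with medical monitor agreement and re-consent. Section 8.4.3 describes a recurrent AE as one that resolves and later comes back.

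**The concern.** There are two separate faults in one paragraph.

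**Pending result.** The trigger and the waiting period are the same for the hold and for the permission to dose, and nothing says who may dose or when. Two sites can act in opposite ways on the same dipstick result and both be compliant.

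**Permanent stop.** A site that follows 6.3.1 literally could treat a second drug-related episode as one from which dosing resumes, possibly at the same dose. Section 6.3.3 ends treatment at that point unless its benefit exception is used, and that exception carries safeguards that 6.3.1 does not mention.

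This is a dose-escalation study run in two countries, so subject safety and consistent handling across sites are at stake. There is a weaker link to the primary endpoint, because interruption days feed the DLT definition and missed doses feed DLT evaluability.

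**Working it through.** The protocol gives no figure of its own on this point. The check is a comparison of text, followed by arithmetic on the possible knock-on to DLT data.

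**1. Which pending-result instruction was meant?** The sentences that follow do not settle it. Resuming after a result below 2 g fits a hold during the wait. Starting to withhold at 2 g or more fits dosing during the wait. Table 6 allows latitude at Grade 2, but 6.3.2 refers kidney toxicity back to 6.3.1. Elsewhere the protocol does write a conditional rule for a pending examination: Table 5, Grade 1 eye toxicity, withholds treatment only if the examination cannot be done within 7 days.

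**2. Episode count.** Episode number = recurrences + 1.

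| Section | Trigger | Recurrences | Episode |
|---|---|---|---|
| 6.3.3, read with 8.4.3 | recurrent, 3D185-related | 1 | 2nd |
| 6.3.1, literal | second recurrence, no causality condition | 2 | 3rd |

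The difference is one episode, with 6.3.1 the later.

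**3. Doses missed during the wait.** Inputs:

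- Planned doses in the DLT window (4.1): 1 + 28 = 29.
- Evaluability limit (4.1): 75% × 29 = 21.75, so 22 doses are needed and at most 7 may be missed.
- Assumed wait *w*: a 24-hour collection started at once or up to 72 hours later, so 1 to 4 days. If the 72 hours in Table 3 note 7 and Section 7.4.1.3 means completed, *w* is 1 to 3 days. Laboratory turnaround is not given and would add to it.

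| *w* (days) | One hold: 29 − *w* | Two holds: 29 − 2*w* |
|---|---|---|
| 1 | 28/29 (97%) | 27/29 (93%) |
| 2 | 27/29 (93%) | 25/29 (86%) |
| 3 | 26/29 (90%) | 23/29 (79%) |
| 4 | 25/29 (86%) | 21/29 (72%) |

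Only two 4-day holds fall below 22 doses. This could happen to a subject who is 2+ or more at both C1D8 and C1D15. One route is enrolment with a baseline of 2+ or more and 24-hour protein below 1 g, which the inclusion criteria allow. Another is new proteinuria that persists.

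**4. DLT status.** Let *h* be the whole days of hold after a result of 2 g/24 h or more. Total interruption is *w* + *h* if the wait is held and *h* if it is dosed. The DLT call differs when only the first total crosses the threshold.

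- Clause in 4.5 (7 days or more): 7 − *w* ≤ *h* ≤ 6. For *w* = 1, *h* = 6; for *w* = 4, *h* = 3 to 6.
- Wording in 6.3.2 (more than 7 days): 8 − *w* ≤ *h* ≤ 7. For *w* = 1, *h* = 7; for *w* = 4, *h* = 4 to 7.

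This matters only for drug-related proteinuria below Grade 3, because drug-related Grade 3 or higher is already a DLT. A hold starting at C1D8 or C1D15 leaves 21 or 14 days of cycle 1. One starting at the C1D28 visit, at its earliest C1D25, leaves 4 and cannot reach 7. The calculation assumes one continuous interruption, which 4.5 does not specify. It also leaves aside a hold starting at C1D1, after the single dose, for which 6.3.1 gives no separate rule.

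**The case against.** The strongest reply on the pending result is that the text is a default hold with permission to dose. On that reading the later sentences fit together: resuming applies to those who were held, and withholding at 2 g or more applies to everyone. Different handling by two investigators is then ordinary discretion. This reading is coherent and may be what was intended. But 6.3.1 does not state it and gives no basis for exercising the discretion, so the need for a clear sentence stands.

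On the permanent stop, the reply is that *second recurrence* may be a slip for second occurrence, in which case the sections agree, and that 6.3.3 is mandatory in any case. Both points are fair. Nothing in 6.3.1 authorises a site to override 6.3.3. The error is that the paragraph a site would consult for proteinuria gives a later trigger.

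The reply is also right that the triggers differ in scope. Section 6.3.3 covers 3D185-related events only, while 6.3.1 has no causality condition. A reader might infer that 6.3.3 already ends treatment at any second result of 2+ or more. It does not, and Section 8.4.2 does not count an unworsened baseline finding as an AE. Simply shortening *second recurrence* to *recurrence* would therefore add a stop for unrelated proteinuria that 6.3.3 does not require.

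**Conclusion.** Both inconsistencies are in the current text and should be corrected on grounds of subject safety and consistent conduct across sites. The size is one episode for the permanent stop, read literally, and 0 versus about 1 to 4 missed doses per hold for the pending result, under the assumed wait and before laboratory turnaround.

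A reader might infer that the DLT data, and so the MTD, are compromised. The documents do not support that. DLT status changes only when a sub-Grade 3, drug-related hold falls just short of the 7-day threshold. Evaluability is lost only with two holds at the top of the assumed range; with waits of up to 3 days, two holds still leave 23/29 (79%). The protocol gives no proteinuria rate, so the frequency of these cases cannot be estimated.

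**What to change.** Both changes are to wording in Section 6.3.1.

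**(a) Permanent stop.** Replace the second-recurrence condition with: if 3D185-related Grade ≥2 proteinuria recurs after resolution (second episode). Keep the nephrotic syndrome stop and refer to the benefit exception in 6.3.3. This adds no stop beyond 6.3.3, and none for unrelated or unchanged baseline proteinuria. Because 6.3.1 now has no causality condition, the change also drops its literal stop at a third unrelated episode. If the sponsor wants that stop, it should be kept as a separate clause.

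**(b) Pending result.** Keep only one instruction, with the sponsor confirming which was intended.

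- *If the hold:* apply it once per episode, at the first new or worsened result of 2+ or more. Do not repeat it for persistent proteinuria already shown to be below 2 g/24 h, or apply it to an unchanged baseline of 2+ or more. A rule that held at every new or worsened result could catch a persistently positive subject twice, leaving 21/29 doses (72%) with two 4-day waits; one 4-day hold leaves 25/29 (86%). The cost is about 1 to 4 missed doses under the stated assumption, plus laboratory turnaround, including in subjects whose result proves to be below 2 g/24 h.
- *If continued dosing:* delete the initial instruction to withhold and start the hold only at 2 g/24 h or more. This misses no doses during the wait, but doses through it in subjects who then need a hold.
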